# General Modeling Considerations for Efficacy Analyses

Unless otherwise specified, efficacy analyses will fit a mixed longitudinal model with change from baseline to each post-baseline month for a response variable, low or high functioning group and age group as stratification variables, OT or placebo treatment group as the between-subjects factor, month as a within-subjects factor, treatment by month interaction, and baseline as a covariate. We will choose between two kinds of models: (1) a random coefficients model treating month continuously with random coefficients for the intercept, slope, and slope squared, and an unstructured covariance matrix among them, and (2) an mixed model with repeated measures (MMRM) treating month categorically and examining unstructured, Toeplitz, autoregressive, and compound symmetric covariance structures among months. We will choose among these candidate models using an information criterion (AIC) while remaining blind to the significance of the treatment effect to avoid bias in the choice of model. Distributional assumptions will be examined using residuals. These mixed models could fail to converge or encounter difficulties based on their use of asymptotics. If they do, we will attempt to simplify the models in order to eliminate the problems, and if necessary, move to analyses that assume compound symmetry, but use a Huynh-Feldt correction if compound symmetry fails.

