#### 1.2 STUDY OBJECTIVES

#### 1.2.1 PRIMARY OBJECTIVE

 To determine the efficacy of intranasal oxytocin (OT) for the treatment of deficits of reciprocal social behaviors in child or adolescent participants with autism spectrum disorders (ASD) as measured by changes in the Aberrant Behavior Checklist- Social Withdrawal Scale (ABC-SW).

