#### 1.2.2 SECONDARY OBJECTIVES

- To determine the efficacy of OT as measured by changes in ABC-SW scores as a function of baseline plasma oxytocin levels, age and functional level and the interaction of each with treatment, and with treatment and week.
- To determine the safety and tolerability of OT in participants with ASD as measured by incidence of treatment emergent adverse events (TEAEs) and abnormal laboratory values, tolerability of OT dose, and time to early termination.
- To determine the efficacy of OT as measured by changes in the sociability factor (SF), a combined measure formed from 13 items of the ABC-SW and the Pervasive Development Disorders Behavior Inventory –Screening Version (PDDBI-SV).
- To determine the efficacy of OT as measured by changes in ABC-SW scores in low-functioning and highfunctioning strata separately.
- To determine the efficacy of OT as measured by changes in Social Responsiveness Scale Version 2 (SRS-2) Social Motivation scores and Stanford Binet-5 Abbreviated IQ standard scores.

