#### 2.3 Sequence of Planned Analyses

All analyses described in this SAP will be performed after data collection has concluded, the database locked, and the treatment blind has been broken. There will be no interim analyses of study data except for the summaries provided to the Data Safety Monitoring Board (DSMB).

An independent DSMB will meet twice yearly to review safety information for the study. The study's DSMB statistician will prepare summaries of data as described in the Safety Analyses section, separating them into treatment group A and treatment group B and will distribute them only to the members of the DSMB. No study team member other than the DSMB statistician will see the summaries provided to the DSMB.

Analyses for the primary manuscript as described in this SAP will focus on analyzing data during the 24-week double-blinded treatment period. Analyses on open-label treatment period (24-48 weeks) and the off-treatment follow-up period (>48 weeks) will be specified in separate analysis plans.

When performing analyses for the primary efficacy variable (ABC-SW), additional models with baseline serum oxytocin, age, and functionality as covariate will be examined and tested prior to analyzing data on the secondary efficacy variables.

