#### 4.2 General Modelling Considerations for Efficacy Analyses

Unless otherwise specified, the primary model is mixed model with repeated measures (MMRM), with change from baseline to each post-baseline timepoint for a response variable, functioning (low versus high) as the stratification variable, center as a blocking factor, treatment (oxytocin versus placebo), week as a continuous variable, treatment and week interaction, and baseline value as a covariate, with random coefficients for the intercept and week, with an unstructured structure among the random coefficients. We will investigate the interaction of treatment, week, and functioning and adopt the most parsimonious model as the final model. Distributional assumptions will be examined using residuals. These mixed models could fail to converge or encounter difficulties based on their use of asymptotics. If they do, we will attempt to

simplify the models in order to eliminate the problems, and if necessary, move to analyses that assume compound symmetry, but use a Huynh-Feldt correction if compound symmetry fails.

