### 4.4 Primary Efficacy Analysis

The primary efficacy response variable will be tested at the level of  $\alpha$  = 0.05. Longitudinal models as described in General Modeling Considerations will be fit with dependent variable of change from baseline to each post-baseline timepoint (weeks) up to week 24. The primary hypothesis test of interest will be a test of treatment effect at week 24.

As a sensitivity analysis, the primary efficacy analysis will also be conducted in the per-protocol population.

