#### 4.5 Subgroup Analysis for Primary Efficacy Variable

As a secondary analysis for the primary efficacy variable, the interaction of treatment-by-functionality-by-week will be examined. In addition, the primary efficacy variable will be analyzed within the low and high functioning stratum separately.

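### Age group is a randomisation stratum but is missing from the SAP 4.2 primary model; a smaller gap is that 4.2 leaves the treatment-week-functioning interaction, and the week-24 contrast that follows from it, open

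*Combined protocol and SAP*

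**What the plan says.** **Strata.** SAP v2.0, 1.3 randomises 1:1 within six strata, three age groups (3-6, 7-11, 12-17) by two functioning levels. The protocol's Randomization Method paragraph and the High Level Summary of Protocol Changes agree that age group was a stratum. Protocol 4.5.1 says both that age is and that it is not a stratification factor, but the more specific Randomization Method text settles on six strata.

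**Primary model.** SAP 4.2 lists functioning, center, treatment, continuous week, treatment-by-week and baseline, with random intercept and week. Center, which was not a stratum, is in; age group, which was, is not. Protocol 10.1 has no age term either. Age enters only through the additional models in 2.3 and 4.6.

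**Accounts of the removal.** Item 17 of the Summary of Changes to the SAP records that age group was taken out of 4.2 and gives no reason. Item 4 of the 2021 Clarifications says it was dropped from the final analysis model because it was not significant. Item 5 of the Summary of Changes adds that age group, not age in months, was used in the covariate models.

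**Interaction.** After stating the base model, 4.2 says: "We will investigate the interaction of treatment, week, and functioning and adopt the most parsimonious model as the final model". Section 4.5 lists the same term as secondary ("the interaction of treatment-by-functionality-by-week will be examined"), and 2.3 treats functionality models as extra ("additional models with baseline serum oxytocin, age, and functionality as covariate will be examined"). On timing, 2.3 says: "All analyses described in this SAP will be performed after data collection has concluded, the database locked, and the treatment blind has been broken". Section 4.4 sets the test: "The primary hypothesis test of interest will be a test of treatment effect at week 24".

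**The concern.** Stratified randomisation balances the arms on age group, so whatever variation age group explains is removed from the true sampling error of the treatment difference. A model without age group still counts that variation as noise. Its standard error is then too large, its interval too wide and its test conservative. The trial would have paid for the balance and not collected the precision. The 2021 reason adds a separate worry: keeping or dropping a design factor according to its own p-value is a data-dependent choice.

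For the interaction, nothing says what makes a model the most parsimonious: no p-value, no information criterion, no hierarchy. If the three-way term stays, the week-24 effect differs between functioning levels, and 4.4 does not say which combination of the two is tested at 0.05. The choice falls after the treatment codes are known.

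**Working it through.** **1. The SAP's own figure.** Section 6 inputs: difference 5, SD 9, two-sided alpha 0.05, power 90%. n per group = 2(1.960 + 1.282)² × 81/25 = 68.1, so 69; the exact t-test gives 69.06, so 70. The SAP states 71, within 2 patients; power at 71 is 0.908. 4 × 71 = 284, as stated. 284/0.99 = 287 against 290 stated. No figure is in dispute.

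**2. Leaving out age group.** Let R² be the share of the residual variance of the week-24 estimate that age group explains. The documents do not give it, so 2%, 5% and 10% are assumed. With balance within strata, the true SE is √(1−R²) times the SE the unadjusted model reports. The interval is therefore too wide by 1/√(1−R²), and true alpha = 2Φ(−1.96/√(1−R²)).

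| R² | CI width factor | True alpha |
|---|---|---|
| 2% | 1.010 | 4.8% |
| 5% | 1.026 | 4.4% |
| 10% | 1.054 | 3.9% |

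Power for a difference of 5 with 142 per arm: SE = 9√(2/142) = 1.068, and Φ(5/1.068 − 1.96) = 0.997. With R² = 10% it is 0.998 without age group and 0.999 with it. At a smaller difference of 3 (an assumption, not a SAP value) the two are 0.81 and 0.84.

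**3. The open interaction.** Taken from the documents: SD 9 at week 24, six post-baseline visits (weeks 4 to 24), linear week, random intercept and slope. Assumed: 72 children per arm per functioning level (288 in all), no true effect, and five sets of (intercept variance, residual variance, covariance): (30, 25, 0), (50, 20, 0), (20, 35, 0), (40, 25, −0.3), (25, 20, 0.3). The slope variance is solved so that total variance at week 24 is 81, giving 0.019 to 0.053. There were 2 million draws per set. The interaction is kept if the between-stratum difference in treatment slopes has |z| > 1.96 (p < 0.05) or |z| > 1.414 (AIC); with no true interaction that happens in 5% or 16% of trials.

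| Reading if the term is kept | Kept at p < 0.05 | Kept by AIC |
|---|---|---|
| Week-24 contrast averaged over functioning | 5.0% | 5.0% |
| Effect read at one functioning level | 5.3-5.7% | 5.5-6.2% |
| Success in either stratum counts | 5.8-6.5% | 6.7-8.0% |

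With equal strata the averaged contrast is the same whether or not the term is kept and is independent of the between-stratum difference, so it stays at 5.0%. Reading one level also widens the interval by √2: SE 9√(2/72) = 1.50 against 9√(2/144) = 1.06.

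These ranges depend on retention being judged on the slope difference. If it is judged on the week-24 stratum difference itself (71 per arm per stratum), the second row becomes 6.5% (p < 0.05) or 7.3% (AIC-like, p < 0.157), and the third row 8.0% or 10.3%.

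**4. Cost of averaging.** With 142 and 148 children (the 142 minimum per stratum, N 290), equal against size weights gives √(0.25 × (1/142 + 1/148) × 290) = 1.0002, an SE 0.02% larger.

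**The case against.** The age-group removal was deliberate and recorded, the protocol model agrees with it, it is conservative, and power is about 0.997. All of that stands: this is neither an oversight nor a threat to validity. What remains is that the two accounts of the removal differ and that the remedy is almost free.

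On the interaction, the SAP points to one overall test. The primary objective is stated for all participants ("To determine the efficacy of intranasal oxytocin (OT) for the treatment of deficits of reciprocal social behaviors in child or adolescent participants"), the stratum results are a secondary objective ("To determine the efficacy of OT as measured by changes in ABC-SW scores in low-functioning and highfunctioning strata separately"), and section 6 says the primary objective uses everyone. That also stands, and it is why 5.0% is the figure to rely on.

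Two stronger readings are tempting. A reader might infer that v2.0 lost a safeguard, because SAP v1.0 chose models "using an information criterion (AIC) while remaining blind to the significance of the treatment effect". The documents do not support that. The v1.0 criterion chose between a random-coefficients model and an MMRM and among covariance structures; it never governed a treatment-by-functioning interaction. Version 2.0 names one model, so that choice no longer exists, and v1.0 likewise placed its analyses after unblinding. A reader might also infer that treatment-by-week could be dropped for parsimony. Section 4.2 names it in the base model and puts only the three-way interaction under investigation.

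One caveat: item 19 of the Summary of Changes to the SAP mentions added SAS detail. None appears in the v2.0 text available, and some pages after section 6 were removed from the copy reviewed. The contents list shows only References there, so code defining the contrast is unlikely but cannot be excluded.

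**Conclusion.** The age-group point holds and is the main one. A stratification factor is missing from the primary model, at the price of a confidence interval 1.0% to 5.4% wider and true alpha of 4.8% to 3.9%, for an assumed R² of 2% to 10%. A reader might infer that the omission biases the effect or inflates error; the direction is the opposite. A reader might also infer from the 2021 clarification that the factor was dropped after someone saw its influence on the treatment result. The documents say only that it was not significant, so the two accounts need reconciling and no more than that can be concluded.

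The interaction point holds as a smaller gap in pre-specification. Type I error is 5.0% under the likely reading. The figures of about 5.3-6.2% (one level read) and 5.8-8.0% (either stratum counts) belong to readings the SAP text weighs against, and they rest on assumed covariances, assumed retention rules and a slope-based retention test. No inflation has been shown.

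**What to change.** 1. **SAP 4.2, model.** Add age group (3 levels) as a fixed factor beside functioning and center, and state that no term is removed for non-significance. Cost: two degrees of freedom.
2. **SAP 4.2, interaction.** Delete the sentence on the most parsimonious model. The three-way interaction stays in 4.5 as secondary, so nothing is lost.
3. **SAP 4.4.** Define the primary test as the week-24 treatment contrast averaged over functioning. Cost: wording, and an SE 0.02% larger than with size weights.
4. **SAP 4.6.** State how the age-group factor combines with the age term, given the declared use of age group in place of age in months.
5. **Records.** Reconcile item 17 of the Summary of Changes with item 4 of the Clarifications on why age group was removed, and the two statements on age stratification in protocol 4.5.1.

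The provision in 4.2 for simplifying a model that fails to converge is left as it stands, so one model choice after unblinding remains possible.

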#### 1.3 STUDY DESIGN

This is a multicenter, randomized, double-blind, stratified, flexible dose, placebo-controlled study designed to evaluate OT in participants with ASD. OT will be given as an intranasal preparation with two different

[figure not shown]
concentrations of 8 IU per insufflation or 24 IU per insufflation. Oxytocin will be administered daily, in single doses up to 40 IU or divided doses in the morning and early afternoon as described in the protocol. Total daily dose is flexible, between 8 IU and 80 IU per day.

Participants who successfully complete screening and baseline assessments and are deemed eligible will be randomized to OT or placebo treatment in a 1:1 ratio, stratified by age group (3-6, 7-11, 12-17) and functioning (low, high), for a total of 6 strata. Randomization will not be stratified by center, as it was felt that additional stratification by center would lead to too many strata, a loss of degrees of freedom, and the potential for a grossly unequal randomization to treatments.

A schematic representation of the study design is shown in Figure 1. After screening and randomization at week 0 (W0), participants enter a double-blind treatment period of 24 weeks (W24), followed by open-label treatment with OT for 24 weeks, termination of OT at the end of week 48 (W48), and a week 53-55 (W53-55) or week 72 OFF treatment follow-up. Although the study design requires patient follow-up from week 0 to week 53-55, this SAP focuses on data analyses for the double-blind treatment period (week 0 to week 24).

Efficacy, safety, and tolerability are measured every four weeks throughout the treatment period. Participants who terminate early are asked to provide safety data through the remainder of the study. The schedule of assessments is provided in Table 1.

Figure 2: Schematic Representation of the Study Design

\*indicates safety labs and genetic sample taken. Primary outcome assessed at bolded time points.

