### 2.2 General Summarization of Study Data

Unless otherwise specified, continuous variables will be summarized with descriptive statistics including n, mean, standard deviation (SD), median, first quartile (Q1) and third quartile (Q3) and minimum and maximum values. Categorical variables will be reported as number and percentage of participants in each category. Least squares (LS) means, standard errors, estimates of contrasts with 95% confidence intervals (CI), and p-values will be reported as appropriate.

All other statistical tests and confidence intervals will be 2-sided, unadjusted for multiplicity, and tested at  $\alpha$  = 0.05, except those explicitly stated to be otherwise.

All analyses and summaries will be produced using SAS® version 9.3 (or higher).

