#### 6. SAMPLE SIZE AND STATISTICAL POWER CONSIDERATION

We will use a mixed longitudinal model for our primary analyses (see Efficacy Analyses section). Since some aspects of the model such as covariance structure are unknown, we performed power and sample size calculations using a more conservative, simplified model corresponding to a two-group t-test on change scores. SOARS-B is powered to allow independent evaluation of oxytocin efficacy in low and high-functioning youth.

Standard deviations of change scores for the ABC-SW range from  $^{\sim}5$  to 9 in several large ASD intervention trials (Shea 2004; McCracken 2002; Owen 2009; Marcus 2009, [name] 2009; Aman 2009). We consider a between groups difference of 5-7 points in ABC-SW change scores to be clinically meaningful. In our power calculations, we use conservative estimates of 9 points for the SD of ABC-SW change and 5 points for between group differences in ABC-SW changes (differential improvement on  $^{\sim}1/3$  of items). To achieve 90% power with an alpha of 0.05 on the ABC-SW, we will require 71 participants in each treatment group within the two strata. Thus, our total required sample to evaluate the ABC-SW separately in low and high-functioning strata is 284. A sample size of 300 will allow for 5% attrition between randomization and the first post-randomization visit. On 3/28/2016, the study team reduced the attrition rate to 1% based on attrition observed in the study, which gives a final sample size of 290. The primary objective considers all participants, resulting in much greater power than for analyses in separate strata.

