Standard deviations of change scores for the ABC-SW range from ~5 to 9 in several large ASD intervention trials (McCracken, McGough et al. 2002; Shea, Turgay et al. 2004; Aman, McDougle et al. 2009; [name], Hollander et al. 2009; Marcus, Owen et al. 2009; Owen, [name] et al. 2009). We consider a between groups difference of 5-7 points in ABC-SW change scores to be clinically meaningful. In our power calculations, we use conservative estimates of 9 points for the SD of ABC-SW change and 5 points for between group differences in ABC-SW changes (differential improvement on  $\sim 1/3$  of items). To achieve 80% power with an alpha of 0.025 on the ABC-SW, we will require 71 participants in each treatment group within the two strata. Thus, our total required sample for the ABC-SW in Aim 1b is 284. We examined change in the combined social score in 30 3-17 year olds with ASD, 20 treated with aripiprazole and 10 medication-free controls. The mean baseline value was 33.5 (17.2 SD) and the change overall was -10.7 (SD 13.0), with a SD of change in each group of 11.9. Within each treatment group, changes in the combined social score paralleled those in the ABC-SW and PDDBI-SV, but had less variability ([name], personal data). We consider a between groups difference in the combined social measure changes of 10-12 to be clinically meaningful. Conservative estimates using a SD of 15 and a between groups difference of 10 in the combined social score changes results in a larger effect size for the combined social measure than for the ABC-SW. Consequently, we should have at least 80% power. A sample size of 300 will allow for 5% attrition between randomization and the first post-randomization visit. On 3/28/2016 we reduced the attrition rate to 1% based on attrition rate observed to date which gives a final sample size of 290. Aims 1a, 3 and 4 consider all participants, resulting in much greater power than for Aim 1b. The power of moderator analyses depends on the distribution of participant characteristics and variability in methylation and mRNA expression observed, which can't be estimated reliably at this time.

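### The compound-symmetry fallback with a Huynh-Feldt correction cannot protect the week-24 treatment contrast; its type I error could lie anywhere from about 5% to about 15%, depending on a covariance the documents do not give

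*Combined protocol and SAP*

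**What the plan says.** SAP v2.0 section 4.2 makes the primary model a longitudinal mixed model for change from baseline. Week is continuous, and the random intercept and random slope have unstructured covariance. If this fails to converge or runs into other difficulties, the team first simplifies it. The last step is: "if necessary, move to analyses that assume compound symmetry, but use a Huynh-Feldt correction if compound symmetry fails". Section 4.4 defines the primary test as the treatment effect at week 24, at the 0.05 level. Section 4.7 applies the same model to the key secondary variables, with a t-test for those measured only at baseline and week 24.

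Protocol v6.0 section 10.1 carries the same fallback clause, but its primary model is different: week is categorical, with a first-order autoregressive covariance.

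Neither document says which error term the fallback would use for the week-24 difference, whether week would stay continuous, or how Huynh-Feldt would apply to a single-degree-of-freedom comparison of arms. On variability, the protocol says only: "Standard deviations of change scores for the ABC-SW range from ~5 to 9 in several large ASD intervention trials". SAP section 6 adds that the covariance structure is unknown.

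**The concern.** Huynh-Feldt was devised for repeated-measures F tests on within-subject effects. It multiplies their degrees of freedom by an estimate of epsilon. The week-24 difference between arms has one degree of freedom, and its validity depends on the standard error. Under compound symmetry that standard error assumes the same variance at every visit and the same correlation between every pair of visits. If children diverge over time, the variance at week 24 exceeds what compound symmetry assigns to it, so the test is anti-conservative.

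The clause invokes Huynh-Feldt precisely when compound symmetry fails. That is when the week-24 standard error is wrong, and the correction does not touch it. At stake is the type I error of the primary test, and of any secondary test under the same model, whenever the fallback is reached.

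**Working it through.** **Inputs from the documents.** SAP section 6: "we use conservative estimates of 9 points for the SD of ABC-SW change and 5 points for between group differences in ABC-SW changes" and "To achieve 90% power with an alpha of 0.05 on the ABC-SW, we will require 71 participants in each treatment group within the two strata". SAP section 2.2 makes tests two-sided, section 1.3 gives 1:1 allocation, and section 6 gives 290 children, so 145 per arm. SAP section 2.1.3 lists six post-baseline ABC-SW visits: weeks 4, 8, 12, 16, 20 and 24.

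**The plan's own figure.** n = 2(1.960 + 1.282)² × 9²/5² = 68.1, so 69 per group (70 with the t distribution). Power at 71 is 91.2% (normal) or 90.8% (t). The stated 71 and 90% are sound. The plan states no error rate for the fallback.

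**Assumption.** The covariance among visits is not given. I fix the week-24 SD at 9 and divide the variance of 81 among intercept, slope and residual, with slope share 0-60% and residual share 10-40%. Autoregressive and rising-SD structures are tried as well.

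**One case in full (continuous week; residual 30%, slope 40%, intercept 30%).**
- Components at week 24: intercept 24.3, slope 32.4 (32.4/24² = 0.05625 per week²), residual 24.3.
- The fitted week-24 value weights each visit by 1/6 + 10(t − 14)/280. The squared weights sum to 0.5238.
- True variance of one child's fitted value: 24.3 + 32.4 + 24.3 × 0.5238 = 69.4.
- Variance of a child's mean over visits: 24.3 + 0.05625 × 14² + 24.3/6 = 39.4. Average visit variance: 48.6 + 0.05625 × 242.67 = 62.25.
- Compound symmetry estimates the within-child variance as 6 × (62.25 − 39.375)/5 = 27.45 and the between-child variance as 39.375 − 27.45/6 = 34.8.
- It therefore assigns 34.8 + 27.45 × 0.5238 = 49.2.
- Ratio of true to assigned SE: √(69.4/49.2) = 1.188.
- Within-subject df are 288 × 5 = 1,440, critical value 1.9616. Rejection rate: 2[1 − Φ(1.9616/1.188)] = 9.88%.
- With Huynh-Feldt (epsilon 0.95, df 1,368): 9.87%. At the lowest possible epsilon (df 288, critical value 1.9682): 9.76%.

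The correction does essentially nothing to this test.

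**Across the assumed range, with Huynh-Feldt.**

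| True covariance | Continuous week | Categorical week |
|---|---|---|
| Slope share 0% | 5.0% | 5.0% |
| Slope share 20% | 6.8-7.1% | 6.5% |
| Slope share 40% | 9.2-10.3% | 8.5-8.6% |
| Slope share 60% | 12.7-15.1% | 11.3% |
| AR(1), constant variance, lag-1 correlation 0.5-0.9 | 6.8-9.2% | 5.0% |
| AR(1) conditional on baseline, same correlations | 10.2-15.9% | 5.7-10.5% |
| SD rising linearly from 5 to 9 | 11.4-15.5% | 12.0% |

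A test using each child's own fitted week-24 value held 4.7-5.5% in simulation (6,000 trials per setting). A plain week-24 comparison of arms held 4.8-5.4%.

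**Does the trigger matter?** Take an estimated slope covariance that is not positive definite as a proxy for non-convergence, with residual share 30%. It occurs in 53%, 22% and 7% of simulated trials at slope shares of 0%, 5% and 10%. In those trials the compound-symmetry test rejects 4.9%, 4.8% and 4.3%. At slope shares of 20% and 40% it occurs in 0.6% and 0.02% of trials, too few to estimate a rate.

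**SRS-2 Social Motivation.** In the double-blind phase the protocol collects it at baseline, week 12 and week 24, giving two change scores per child. Their covariance matrix has three elements. The specified model has four covariance parameters: two variances, their covariance and the residual. It cannot be identified, whatever the slope variance.

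If the simplification ends in compound symmetry, the SE ratio is √[2r/(1 + r)], where r is week-24 variance over week-12 variance. For assumed r of 1.25, 1.65 and 3.24 the ratios are 1.054, 1.116 and 1.236, and the rejection rates 2[1 − Φ(1.96/ratio)] are 6.3%, 7.9% and 11.3%. With two visits epsilon is always 1, so Huynh-Feldt has no effect at all.

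**Limits.** The data are balanced and complete, and baseline, centre and stratum covariates are not simulated.

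**The case against.** The strongest reply is that this is a last resort and mostly harmless when reached. For a random-slope model the commonest fitting failure is a slope variance estimated at or near zero, and compound symmetry is then nearly true. The conditional rates of 4.3-4.9% bear this out. A reader might infer that the primary test would reject far above 5% whenever the fallback is used; the documents do not support that. This part of the objection stands for that trigger. It does not close the matter, because the SAP's trigger also covers unspecified difficulties, and the SRS-2 case forces simplification regardless of slope size.

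A reader might also take the cited SD range of 5 to 9 as evidence that the SD grows over the 24 weeks. It is not. It describes spread across different trials, so the rising-SD rows are assumptions.

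Nor do the documents establish that the fallback discards every child with a missed visit. That would follow from classical repeated-measures ANOVA, which the Huynh-Feldt wording suggests but the SAP does not name. If that form were paired with a separate week-24 ANOVA, the week-24 test would hold 5%.

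Finally, under the protocol's own model (categorical week, AR(1), constant variance) the fallback holds 5.0%. Inflation there needs variance that grows with time.

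**Conclusion.** The point holds as a defect in a stated rule. Huynh-Feldt cannot do what the clause asks of it for the week-24 contrast, and the error term for that contrast is left undefined. The type I error could be about 5% (compound symmetry true, slope variance near zero, or categorical week with constant variance) or about 15% (large slope variance or strongly rising SD; 15.9% at the most extreme setting tried). Where in that range it falls depends on a covariance that the documents call unknown.

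For the primary outcome the fallback may never be reached, and it may be benign if it is. For SRS-2 Social Motivation some simplification is certain, but compound symmetry is not the only possible end: dropping just the intercept-slope covariance would leave three parameters for three elements. The 6-11% applies if compound symmetry is chosen, under the assumed variance ratios. This should be corrected, but it does not show that the planned primary analysis is invalid.

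**What to change.** In SAP section 4.2 and protocol section 10.1, delete the Huynh-Feldt clause. In its place state one of two rules: either any simplified or compound-symmetry fit will test the week-24 contrast with an empirical (sandwich) standard error, or the fallback is an ANCOVA of week-24 change on baseline with the same covariates. For outcomes with two post-baseline visits, such as SRS-2 Social Motivation, specify categorical week with a 2x2 unstructured covariance from the start.

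A mandatory sequence of unstructured and Toeplitz fits is not needed: a six-visit unstructured matrix has 21 parameters, against four in the model that failed.

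The cost is wording, a little programming and slightly wider intervals. The ANCOVA uses only children with a week-24 score, and the sandwich standard error does not remove bias from outcome-dependent dropout. The missing-data analyses in SAP section 4.3 would therefore still be needed beside either option.
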